- Had a record of active cancer, defined as first diagnosis of cancer with V code (a special code applied to patients with confirmed diagnosis of cancer by Korean Ministry of Health and Welfare for reimbursement for 5 years or longer if recurrent/metastatic) within the past 6 months of period prior to index date; or receiving anti-cancer treatment (chemotherapy, radiation therapy, or cancer-related surgery) under cancer diagnosis with V code within the past 6 months period prior to index date

Follow-up

- **Phase I of the study:** Patients will be followed-up from the index date until the earliest of in-hospital death or end of the study period (31 Dec 2019).
- **Phase II of the study:** Patients will be followed-up from the index date until the earliest of outcome occurrence (bleeding event), treatment discontinuation, switch to another anticoagulant, in-hospital death, or end of the study period (31 Dec 2019), where patients will be considered to have discontinued treatment when new prescription is absent within the 30-day grace period after the end of the former prescription.

- **Variables**

Exposure(s)

- Anticoagulant therapy (PAC [LMWH, UFH, others], NOACs [apixaban, dabigatran, rivaroxaban, edoxaban], warfarin).

Outcome(s)

- **Phase I of the study:** sociodemographic and clinical characteristics of patients with VTE, utilization of index anticoagulant treatment, treatment patterns (including treatment interruption, switching, complete discontinuation), overall treatment duration, and clinical events preceding first treatment change
- **Phase II of the study:** Primary or secondary diagnosis with major bleeding (by site: intracranial, gastrointestinal [GI], and other sites) after the index date

Covariate(s)

- Sociodemographics (age, sex) will be assessed on the index date. Clinical characteristics including comorbidities, previous use of medications, and the number of outpatient visits will be assessed within the 6-month period prior to the index date

- **Data sources**

- South Korea's Health Insurance and Review Assessment Service (HIRA) database

- **Study size**

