8.2. Study population

The study cohort will be defined as patients diagnosed with VTE between 1 Mar 2013 and 30 Jun 2019. The cohort entry will be defined as the date of incident VTE diagnosis. The index date will be defined as the date of first prescription for anticoagulants within 30 days after the index VTE event. The length of the exclusion assessment window will vary depending on the condition, from 12-months at minimum to anytime prior to index date. The following patients will be excluded: A record of VTE diagnosis within the 12-month period prior to the index VTE encounter, diagnosed with atrial fibrillation, atrial flutter, mechanical heart valve replacement or mitral stenosis anytime prior to index date, had a record of Inferior Vena Cava filter anytime prior to index date, received anticoagulatory therapy within the 12-month period prior to index VTE encounter to restrict to new users of anticoagulatory therapy, prescribed two different anticoagulants on the same index date to prevent exposure misclassification, had a record of pregnancy within the 9-month period prior to index date, and for the Phase II of the study only, had a record of active cancer within six months period prior to index date.

Baseline sociodemographic characteristics (e.g., age, sex) will be assessed on the index date, whereas clinical characteristics (comorbidities, previous use of medications, Charlson comorbidity index [CCI], HAS-BLED scores, initial presentation of VTE, number of outpatient visits) will be assessed in the 6-month period prior to the index date except when otherwise specified in section 8.4 *Variables* (Figure 2).

Within this study cohort, we will describe the treatment patterns of anticoagulants prescribed for VTE treatment throughout the period of follow-up, defined as the period from the index date to the end of the study period. Moreover, if feasible, we will also examine the risk of major bleeding overall and by site, associated with each NOAC use, as compared with warfarin.

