8.4. Variables

Exposure

- **Phase I of the study:** PAC (UFH [Anatomical Therapeutic Chemical [ATC] code: B01AB01], LMWH [B01AB04, B01AB05, B01AB06, B01AB12], VKA (warfarin [B01AA03]), NOACs (apixaban [B01AF02], rivaroxaban [B01AF01], edoxaban [B01AF03], dabigatran [B01AE07])
- **Phase II of the study:** Apixaban (B01AF02), Rivaroxaban (B01AF01), Edoxaban (B01AF03), Dabigatran (B01AE07), Warfarin (B01AA03)

Outcome(s)

- **Phase I of the study**

- Sociodemographic and clinical characteristics of patients with VTE who initiated anticoagulants.
- Utilization of different anticoagulants at treatment initiation. Patients will be classified based on their index anticoagulant treatment received within 30 days after being diagnosed with VTE.
- Treatment interruption from the index anticoagulant treatment, which will be defined as when a patient has a gap with no new treatment within 30 days of the estimated end of supply, but subsequently restarts the index treatment after this period.[1] The time to treatment interruption will be defined as the period from the index date to the date of treatment interruption.
- Treatment switching will be defined as a prescription of another anticoagulant therapy that is started after the treatment initiation of the index anticoagulant treatment and within 30 days after the estimated end of supply of the index anticoagulant drug (exposure to the new anticoagulant treatment must last for at least 30 days to be considered as a treatment switch). The time to treatment switch will be defined as the period from the index date to the date of treatment switch.

Exemption: As heparin can be initiated at acute stage of DVT/PE before clinical decision to use OAC, a switch from initial heparin treatment to an OAC within 2 weeks after heparin treatment initiation will not be considered a treatment switch.

- Treatment discontinuation (complete discontinuation; no reinitiation) will be defined as when a patient who ended their first continuous treatment episode with the index anticoagulant treatment without switching, and subsequently have no further prescriptions for that respective anticoagulant treatment during all available follow-up time. The time to treatment discontinuation will be defined as the period from the index date to the date of treatment discontinuation.
- Overall anticoagulant treatment duration will be defined as the time period from the index date to the earliest of treatment interruption, switch, or discontinuation.

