10. STATISTICAL ANALYSIS

All statistical analyses will be performed using SAS Enterprise Guide 7.1 (SAS Institute Inc., Cary, NC, USA), provided by HIRA through a virtual access machine.

Phase I of the study (descriptive)

Main Analysis

- Descriptive analysis will be conducted separately in two cohorts of non-cancer VTE and cancer VTE patients according to co-presence of active cancer.
- Sociodemographic and clinical characteristics will be summarized with means (standard deviations [STD]) or median (interquartile range [IQR]) for continuous variables and with count (proportions) for categorical variables for the three treatment groups of interest: PAC only (UFH, LMWH, UFH+LMWH), warfarin-based (warfarin, PAC/warfarin) group, NOAC-based (NOAC, PAC/NOAC) group. NOAC-based (NOAC, only group, PAC/NOAC) group. Analysis of variance, and chi-square test will be conducted for continuous variables, and categorical variables, respectively.
 - In order to distinguish between PAC bridging therapy and PAC treatment, we will apply a time restriction of 2 weeks to PAC bridging therapy.
- Temporal trend in anticoagulation therapy for VTE will be presented between 1 Mar 2013 and 30 Jun 2019. Proportions of the index OACs will be estimated according to calendar year and quarter.
- The number and percentage of patients who discontinue treatment completely, experience treatment interruption and treatment switch during their follow-up will be described by the index anticoagulant treatment received. Results will be limited to the first of each of these events for each patient. For patients experiencing a treatment switch, the new treatment will be described at the time of their first switcher per individual drug.
- The duration of the index treatment by the index anticoagulant treatment received will also be summarized in terms of days using descriptive statistics (mean [STD], median [IQR]).
- The Kaplan-Meier method will be applied to derive the empirical distribution of time to each of the treatment endpoints of interest (e.g., treatment discontinuation or switch); these analyses will be performed per index anticoagulant treatment received and no comparisons will be made. Log-rank test will be conducted at the 3-, and 6 months after treatment initiation to assess statistical significance between the survival curves. Persistent rate will also be calculated at the same time point.

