13. LIST OF FIGURES

Figure 1. Kaplan-Meier plot showing time to anticoagulant therapy interruption in patients with venous thromboembolism according to presence of active cancer.	65
Figure 2. Kaplan-Meier plot showing time to anticoagulant therapy switching in patients with venous thromboembolism according to presence of active cancer.	66
Figure 3. Kaplan-Meier plot showing time to anticoagulant therapy discontinuation in patients with venous thromboembolism according to presence of active cancer.	67
Figure 4. Trends in newly prescribed anticoagulants in patients with venous thromboembolism between Mar 2013 and Jun 2019.....	68
Figure 5. Cumulative incidence curves for the risk of major bleeding events associated with NOAC use versus warfarin	69
Figure 6. Number of weighted events, incidence rate, and hazard ratio of major bleeding events associated with NOAC use versus warfarin.	70

[figure not shown]

Figure 1. Kaplan-Meier plot showing time to anticoagulant therapy interruption in patients with venous thromboembolism according to presence of active cancer.

[figure not shown]

Figure 2. Kaplan-Meier plot showing time to anticoagulant therapy switching in patients with venous thromboembolism according to presence of active cancer.

[figure not shown]

Figure 3. Kaplan-Meier plot showing time to anticoagulant therapy discontinuation in patients with venous thromboembolism according to presence of active cancer.

[figure not shown]

Figure 4. Trends in newly prescribed anticoagulants in patients with venous thromboembolism between Mar 2013 and Jun 2019.

[figure not shown]

Figure 5. Cumulative incidence curves for the risk of major bleeding events associated with NOAC use versus warfarin

PFIZER CONFIDENTIAL

[figure not shown]

Figure 6. Number of weighted events, incidence rate, and hazard ratio of major bleeding events associated with NOAC use versus warfarin.

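### Phase I plans separate Kaplan-Meier curves for interruption, switch and discontinuation with no competing-risk method or censoring rule, so each curve will overstate the share of patients who have the event

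*SAP*

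**What the plan says.** SAP section 10 (Phase I, Main Analysis) and Protocol section 9.7 give the same method: "The Kaplan-Meier method will be applied to derive the empirical distribution of time to each of the treatment endpoints of interest". SAP section 13 lists one figure per endpoint, for example "Kaplan-Meier plot showing time to anticoagulant therapy interruption in patients with venous thromboembolism according to presence of active cancer" and "Kaplan-Meier plot showing time to anticoagulant therapy discontinuation in patients with venous thromboembolism according to presence of active cancer", with a matching figure for switching. The stated time points for the tests and persistence rates are 3 and 6 months.

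SAP section 8.4 defines the endpoints. Complete discontinuation applies to a patient who "ended their first continuous treatment episode with the index anticoagulant treatment without switching" and has no later prescription of that drug. Interruption is a gap of more than 30 days in a patient who stops "but subsequently restarts the index treatment after this period". A switch is a new anticoagulant started no later than 30 days after the index supply ends.

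On follow-up, Protocol section 4 says: "Patients will be followed-up from the index date until the earliest of in-hospital death or end of the study period". SAP section 8.2 describes it only as "defined as the period from the index date to the end of the study period" and does not name death. Protocol section 9.1 uses the same shorter wording.

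No section gives a censoring rule for the Phase I curves. The only cumulative incidence wording is the title of SAP Figure 5, which concerns Phase II bleeding.

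**The concern.** The three endpoints and in-hospital death compete. A patient whose first episode ended in a switch, or in a gap followed by a restart, cannot meet the discontinuation definition. A patient who has died can have none of the three. Kaplan-Meier treats a censored patient as still able to have the event later. When the reason for censoring is a competing event, one minus Kaplan-Meier estimates the probability in a hypothetical population where the competing event cannot occur. It is not the proportion of patients in whom the event occurs.

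Describing treatment patterns is a primary Phase I objective, and readers will take the curves as the share of Korean VTE patients who stopped, switched or paused. With no stated rule, two programmers could also follow this SAP and draw materially different curves.

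**Working it through.** **Nothing to reproduce.** The documents state no Phase I death, interruption, switch or discontinuation rate. All rates below are assumptions.

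**What can be censored by 3 and 6 months.** Diagnoses run to 30 Jun 2019, treatment starts within 30 days of diagnosis, and data end on 31 Dec 2019. The latest index date is therefore 30 Jul 2019, which leaves 154 days. Nobody reaches the end of the study before 3 months, and only the latest entrants do so before 6 months. At 3 months the only possible censoring is in-hospital death or, if programmed that way, another treatment change. Those are the competing events themselves.

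**Formulas (constant hazards).** For event k with monthly hazard h_k and total hazard H:

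- One minus Kaplan-Meier, all competing events censored: 1 − exp(−h_k·t)
- Cumulative incidence: (h_k/H)·(1 − exp(−H·t))

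**Illustration.** Assumed hazards are discontinuation 0.10, interruption 0.03, switch 0.03 and death 0.05, so H = 0.21.

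- Discontinuation, 3 months: 1 − e^(−0.30) = 25.9%, against (0.10/0.21)(1 − e^(−0.63)) = 0.476 × 0.467 = 22.3%.
- Discontinuation, 6 months: 1 − e^(−0.60) = 45.1%, against 0.476 × (1 − e^(−1.26)) = 0.476 × 0.716 = 34.1%.
- If discontinuation and death are the only events (H = 0.15), 3 months: 25.9% against (0.10/0.15)(1 − e^(−0.45)) = 0.667 × 0.362 = 24.2%.

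**Consistency check.** With the four hazards above, interruption and switch each read 1 − e^(−0.09) = 8.6% at 3 months and 1 − e^(−0.18) = 16.5% at 6 months. The three curves then sum to 43% and 78%. The true probability of any change is (0.16/0.21) × 0.467 = 35.6% and (0.16/0.21) × 0.716 = 54.6%.

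**Range over the death rate and the censoring rule.** Here the assumed 6-month net probabilities are discontinuation 40%, interruption 15% and switch 10%, each converted by h = −ln(1 − p)/6. The middle column keeps patients with another treatment change in the risk set and censors only death, so its value is h_k/H′·(1 − exp(−H′·t)), with H′ the total hazard excluding death. Values are for discontinuation at 6 months.

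| Assumed 6-month death | All competing events censored | Only death censored | Cumulative incidence | Ratios |
|---|---|---|---|---|
| 2% | 40.0% | 35.5% | 35.2% | 1.14 and 1.01 |
| 20% | 40.0% | 35.5% | 32.3% | 1.24 and 1.10 |
| 40% | 40.0% | 35.5% | 28.7% | 1.39 and 1.24 |

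For switch, with all competing events censored, 10.0% compares with 7.3%, 6.7% and 5.9%, up to a ratio of 1.69. A simulation of 400,000 patients in the 20% row agreed with the formulas to within 0.1 percentage point.

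**The case against.** The strongest reply is that no section says other treatment changes are censored. Phase I follow-up does not end at a treatment change, and SAP section 10 says: "Results will be limited to the first of each of these events for each patient". One patient can therefore count under more than one type and may simply stay in the risk set. This stands: a reader might infer that the plan censors the other changes, but that is an inference from the definitions. On the alternative reading only death biases the curves, and the effect is small when in-hospital death is rare (ratio 1.01 at 2%).

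One minus Kaplan-Meier is also a legitimate net quantity, and SAP Tables 5 to 8 already show n (%) for switching, continuation, discontinuation, interruption and death side by side. Both points are fair. But the Phase I objective is to describe what happened to patients, not what would happen if other events were removed, and the table rows do not correct the curves. Since nobody reaches study end before 3 months, simple counts by 3 months would disagree with a curve that censors competing events.

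Three stronger readings are tempting and should not be drawn.

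- *The bias is largest in the active-cancer cohort.* The documents give no rates by cohort, and the ordering can reverse. With interruption 15% and switch 10% in both, the 6-month ratio for switch is 1.38 in a non-cancer scenario (discontinuation 40%, death 2%) but 1.29 in a cancer scenario (discontinuation 15%, death 20%).
- *Kaplan-Meier exaggerates the cancer contrast through mortality.* With a discontinuation hazard of 0.10 and death as the only competing event, one minus Kaplan-Meier at 12 months is 70% whether the death hazard is 0.01 or 0.10. It is the cumulative incidence that moves, from 67% to 45%. The cohorts are in any case to be analysed separately.
- *The curves will sum to more than 100%.* Under the illustrative hazards they reach 130% at 12 months, but 43% and 78% at the plan's own time points.

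**Conclusion.** The concern holds in a limited form. Following the SAP with the protocol's follow-up rule censors at least in-hospital death, so one minus Kaplan-Meier overstates the proportion of patients with each event. If other treatment changes are censored as well, the overstatement is larger. Under the assumed rates the 6-month ratio runs from 1.01 to 1.24 with death alone censored, and from 1.14 to 1.69 across the three endpoints with everything censored. The direction is certain once a competing event has been censored; the size rests on assumed constant hazards. The part due to death is larger in the active-cancer cohort only if in-hospital death is more frequent there. The change should be made because it is cheap and bears on a primary Phase I objective.

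**What to change.** In SAP section 10 and Figures 1 to 3, with matching text in Protocol section 9.7:

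1. Replace the three Kaplan-Meier curves with Aalen-Johansen cumulative incidence for the first of interruption, switch, discontinuation or in-hospital death, by index treatment within each cohort, with values at 3 and 6 months.
2. Keep Kaplan-Meier only for time to any treatment change (persistence), and state how death is handled there.
3. Align the follow-up wording in SAP section 8.2 (and Protocol section 9.1) with Protocol section 4 on in-hospital death.
4. Add a limitation: follow-up captures only in-hospital death. A death outside hospital leaves no further prescriptions and will appear as discontinuation under either estimator.

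The cost is SAP and protocol wording and SAS code. No new data are needed.
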